Preclinical studies of venetoclax and ibrutinib in DLBCL cell lines have shown that higher levels of BCL-2 expression were associated with greater sensitivity to single-agent venetoclax than lower levels. [19] In addition, single-agent ibrutinib increased BCL-2 expression and sensitivity to venetoclax. Pretreatment samples from patients who responded to ibrutinib had lower BCL-2 expression; whereas a high BCL-2 mutation rate was observed in patients who responded poorly to ibrutinib. Concurrent administration of ibrutinib and venetoclax resulted in complete tumor growth inhibition in a DLBCL (activated B-cell subtype) murine model. There are currently no data available from follicular lymphoma clinical trials evaluating the correlation between BCL-2 family members and sensitivity to venetoclax. Similarly, the clinical implications of the pro- and antiapoptotic members of the BCL-2 family have not been evaluated in patients receiving concurrent venetoclax and ibrutinib. Levels of expression of various BCL-2 family member proteins will be assessed on tumor samples prior to treatment, bone marrow biopsy samples after achieving a complete response, and tumor samples at progression in order to understand the implications of these proteins in terms of response to therapy, development of resistance, and the ability to overcome resistance.

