2.3 Exploratory Objectives

- To evaluate mutations of resistance via next-generation sequencing to the regimen when administered in combination in relapsed and refractory follicular lymphoma
- To evaluate for an association between BCL-2 and other family member protein levels of expression and efficacy of the regimen

- To evaluate the feasibility of developing tumor cell cultures from bone marrow aspirates with lymphomatous involvement in order to better characterize activity of the combination

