4.2. Schedule of Events

Table 1: Schedule of Events

All scheduled visits during Cycle 1 can occur +/- 1 day.

All scheduled visits during Cycles 2-12 can occur +/- 3 days if necessary.

For patients who continue on therapy after Cycle 12, scheduled visits and associated testing will occur every 2 cycles (instead of every cycle) with even numbered cycles only (i.e. Cycle 14, 16, etc.) All scheduled visits for patients receiving treatment after Cycle 12 can occur +/- 7 days if necessary.

As the bone marrow biopsy and aspirate are not needed to determine eligibility for trial enrollment, this test has been removed from the screening phase of the study. The bone marrow procedures must be performed after the patient has been provided an official identification subject number, but before the administration of the first dose of study drugs on Cycle 1 Day 1. The bone marrow biopsy at enrollment may be waived per investigator discretion. If a patient achieves a complete response by imaging, a bone marrow biopsy should be performed to confirm a complete response.

	Prior to Cycle 1 Day	Cycle 1 D1, 8, 15, 22	Cycle 2-12 Day1	Even Numbered Cycles after C12	At time of restaging*	Follow- up**
TESTS & OBSERVATIONS						
History and progress notes	X	X	A	X	X	X
Medication History	X	X	A	X	X	
Physical examination	X	X	A	X	X	X
Pulse, blood pressure	X	X	A	X	X	X
Height	X					
Weight/body surface area	X	X	A			
Performance status	X	X	A	X	X	X
Tumor measurements	X	B	B	B	B	B
Solicited baseline abnormalities/ adverse events assessment	X	X	X			
LABORATORY STUDIES						
CBC, differential, platelets	X	X	A	X	X	X
CMP, CrCl (estimated)	X	X	A	X	X	X
Uric acid, LDH, Mg, Phos, Ca	X	X	A	C	C	C
β2-microglobulin	X					
Serum or urine βHCG‡	X		A			
HBsAg, HBsAb, HB core Ab	X					
HCV antibody, HIV	X					
PT/INR, PTT	X					
EKG	X	C	C	C	C	C
Pharmacokinetics		X				
CORRELATIVE STUDIES						
Caris Life Sciences MI Tumor Seek	D					E

BCL-2 Protein Assessment	D				E
Tumor cell cultures	D				
STAGING					
PET-CT	X			X	F
CT/MRI (neck/chest/abd/pelvis)	X				X
Bone marrow aspirate & biopsy	G			H	
Histologic review	X				I

* Restage during week 12 (cycle 3), week 24 (cycle 6), and during week 52 (cycle 13).

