10.2. BCL-2 Family Proteins

Levels of expression of various BCL-2 family member proteins will be assessed on tumor samples from patients prior to treatment, on bone marrow biopsy samples after achieving a complete response, and tumor samples at progression. Assessments will be performed on bone marrow biopsy core samples of patients with lymphomatous involvement. One centimeter of the core biopsy will be submitted to the Lombardi Comprehensive Cancer Center

Histopathology and Tissue Shared Resource (HTSR) for processing. The presence of tumor will be assessed by H&E. Sections will be stained by the HTSR for BCL-2 family proteins including BCL-2, MCL-1, BIM, and BCL-XL. The stained slides will be subsequently transported to the Department of Pathology for H-score assessment of individual BCL-2 family member proteins. Samples will be reviewed independently by two hematopathologists ([name]; [name]). If the bone marrow is not involved, the patient may be recommended to undergo a biopsy of an affected lymph node or other disease-involved area as determined by pretreatment staging PET-CT. Alternatively, if tissue is already available from a recent biopsy of an affected area, it may be submitted. These patients will only undergo a follow up biopsy if they experience a progression on study.

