12.5.2. BCL-2 Family Proteins

Descriptive statistics (including mean, median, std, min, max) will be used to summarize the H-score assessment of individual BCL-2 family member proteins. The H-score will then be categorized, and Fisher's Exact test will be used to explore its relationship with varying expression of BCL-2 family member proteins.

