12.5.3. Tumor Cell Cultures

Evaluate for possible correlations between in vitro sensitivity, patient response, the pattern of BCL-2 family member expression, and the spectrum of gene mutations identified by NGS.

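### The one test in Section 12.5.2 sets BCL-2 family expression against itself and names no efficacy variable, so as written it does not address the second exploratory objective in Section 2.3

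*Combined protocol and SAP*

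**What the plan says.** The second bullet of Section 2.3 sets the objective: "To evaluate for an association between BCL-2 and other family member protein levels of expression and efficacy of the regimen". Section 1.10.2 gives the purpose of the measurements, which is to "understand the implications of these proteins in terms of response to therapy, development of resistance, and the ability to overcome resistance".

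Section 10.2 describes the measurement. Samples are taken before treatment, "on bone marrow biopsy samples after achieving a complete response, and tumor samples at progression". They are stained for BCL-2, MCL-1, BIM and BCL-XL and sent for "H-score assessment of individual BCL-2 family member proteins".

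Section 12.5.2 gives the analysis. H-scores are summarised descriptively. Then "The H-score will then be categorized", and Fisher's "Exact test will be used to explore its relationship with varying expression of BCL-2 family member proteins". No other test of these proteins is stated there.

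The neighbouring sections differ. Section 12.5.1 uses Fisher's exact test to relate clinical outcomes to new genomic alterations. Section 12.5.3, under tumor cell cultures, reads: "Evaluate for possible correlations between in vitro sensitivity, patient response, the pattern of BCL-2 family member expression", followed by the mutation spectrum from sequencing.

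**The concern.** An analysis section should contain the analysis that answers the objective. Here the objective relates expression to efficacy, while the stated test relates a categorised expression score to expression. A statistician following Section 12.5.2 literally would produce a table with no response, progression or survival variable in it.

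The outcome would then have to be supplied later, together with the sampling point and the cut-points, neither of which is stated. If those choices were made once responses were known, in a sample this small, an apparent association would be hard to interpret.

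**Working it through.** **Comparison of the text.** The plan states no figure for this analysis, so the main check is what each section puts on the two sides of the comparison.

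| Section | First variable | Second variable | Method |
|---|---|---|---|
| 2.3, second bullet | BCL-2 family expression | Efficacy of the regimen | (objective) |
| 12.5.1 | New mutations or genomic alterations | Clinical outcomes | Fisher's exact test |
| 12.5.2 | Categorised H-score, i.e. expression | Varying BCL-2 family expression | Fisher's exact test |
| 12.5.3 | BCL-2 expression pattern, among others | Patient response, among others | None stated |

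The second variable in 12.5.2 can be read in three ways:

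1. The same protein's expression. The test is then circular.
2. Another family member's expression. This tests whether proteins vary together and says nothing about efficacy.
3. Change in expression across the three sampling points. Two of these points are defined by outcome (after complete response and at progression), so this reading bears on resistance. It still does not compare pre-treatment expression between patients who respond and those who do not.

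No reading supplies the comparison set by the second bullet of 2.3.

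**Secondary check: the open cut-point.** This applies to the test that would exist once response is named as the outcome.

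Inputs:
- 17 evaluable patients: the phase II size in Section 12.2, assuming every patient has usable baseline tissue.
- Response splits from the design rates in Section 12.2: 17 × 0.60 = 10.2, so 10 v 7; 17 × 0.30 = 5.1, so 5 v 12.
- Two categories, two-sided p ≤ 0.05 (Section 12.5 states no level), no ties, and no true association.

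*Median cut fixed in advance* (8 low, 9 high). The number of responders x in the low group is hypergeometric, P(x) = C(r, x) · C(17 − r, 8 − x) / C(17, 8), with C(17, 8) = 24,310.
- r = 10: p ≤ 0.05 at x = 1, 2, 7 and 8, so (10 + 315 + 840 + 45) / 24,310 = 1,210 / 24,310 = 5.0%.
- r = 5: p ≤ 0.05 at x = 0 and 5, so (495 + 220) / 24,310 = 715 / 24,310 = 2.9%.

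*Cut chosen after seeing response.* Rank patients by H-score, list every arrangement of responders over the ranks, and count those where at least one of the 16 cuts gives p ≤ 0.05.
- 10 v 7: 2,983 of C(17, 10) = 19,448 arrangements, 15.3%.
- 5 v 12: 812 of C(17, 5) = 6,188 arrangements, 13.1%.

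Limiting the search to central cuts (5 to 12 patients in the low group) gives 2,723 / 19,448 = 14.0% and 714 / 6,188 = 11.5%.

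With fewer evaluable patients the effect can vanish. For 12 patients split 4 v 8, the best-of-all-cuts rate is 24 / 495 = 4.8%, below the nominal 5%.

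**The case against.** The strongest reply is that the intent is clear. Section 2.3 states the efficacy link, Section 12.5.1 shows the authors using the same test against clinical outcomes, and Section 12.5.3 lists patient response beside BCL-2 expression. On that view 12.5.2 contains a wording slip, in an exploratory analysis of optional correlative studies (Section 14.2). Most of this stands, and a slip is the likeliest explanation. It does not supply the missing content: 12.5.1 concerns mutations, and 12.5.3 sits under cell cultures and gives no test, outcome definition or H-score categories.

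The change-over-time reading also deserves credit, because it does bear on the development of resistance. It leaves the efficacy objective unanswered.

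The false-positive figures have limits too. They measure the open cut-point in an assumed test, not the missing efficacy variable. Part of each contrast reflects the conservatism of Fisher's test at the median cut, and the 4 v 8 case shows no inflation above 5%.

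A reader might go further and infer that the plan nowhere connects BCL-2 expression with response, or that cut-points are meant to be picked after the results are seen. The documents support neither inference. Section 12.5.3 does mention the two together, and the plan is silent on when cut-points would be set.

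**Conclusion.** The point holds for Section 12.5.2 and the second bullet of Section 2.3. The stated test has expression on both sides and no efficacy variable, so followed as written it cannot meet that objective. This rests on the text alone and needs no numerical assumption.

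The missing cut-points are a lesser, related gap. With 17 evaluable patients the false-positive chance per protein would rise from 5.0% to 15.3% (10 v 7) or from 2.9% to 13.1% (5 v 12) if the cut were chosen after seeing response. Those figures depend on the assumed evaluable number, splits, 5% level and two categories.

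It would be wrong to read this as a threat to the trial's main conclusion. The analysis is exploratory, and the primary analysis, sample size and go/no-go rule do not depend on it. The sentence should be corrected because the stated analysis misses its own objective and the correction uses data already planned.

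**What to change.** Replace the Fisher sentence in Section 12.5.2 with wording such as:

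*For each protein, the pre-treatment H-score, categorised at cut-points fixed before outcome data are examined, will be compared between responders (CR or PR by the Lugano criteria) and non-responders using Fisher's exact test. The number of evaluable patients will be reported for each protein, and the results are exploratory.*

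An exact rank-sum test on the uncut H-score is an acceptable alternative and removes the need for cut-points. Add one sentence stating how the H-scores after complete response and at progression will be used for the resistance question in Section 1.10.2. Whether to pool dose levels, and whether the later samples are tested or only described, is for the investigators to decide and state.

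Cost: one amended and one added sentence, with no extra patients, visits or tissue. As a protocol amendment it needs the supporting company's review and IRB approval (Section 14.1). Estimates will be imprecise, because the baseline marrow biopsy may be waived (Section 4.2, footnote G) and the correlative studies are optional.

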12.5.3. Tumor Cell Cultures

Evaluate for possible correlations between in vitro sensitivity, patient response, the pattern of BCL-2 family member expression, and the spectrum of gene mutations identified by NGS.

13. ADVERSE EVENT REPORTING

Timely, accurate, and complete reporting and analysis of safety information from clinical studies are crucial for the protection of subjects, investigators, and the sponsor, and are mandated by regulatory agencies worldwide.

13.1. Definitions

13.1.1. Adverse Events

An adverse event (AE) is any untoward medical occurrence in a subject administered a pharmaceutical product and which does not necessarily have a causal relationship with this treatment. An AE can therefore be any unfavorable and unintended sign (including a clinically significant abnormal laboratory finding, for example), symptom, or disease temporally associated with the use of an investigational study drug, whether or not considered related to the study drug.

For the purposes of this clinical study, AEs include events which are either new or represent detectable exacerbations of pre-existing conditions.

The term “disease progression” should not be reported as an adverse event term. As an example, "worsening of underlying disease" or the clinical diagnosis that is associated with disease progression should be reported.

Adverse events may include, but are not limited to:

- Subjective or objective symptoms provided by the subject and/or observed by the Investigator or study staff including laboratory abnormalities of clinical significance.
- Any AEs experienced by the subject through the completion of final study procedures.
- AEs not previously observed in the subject that emerge during the protocol-specified AE reporting period, including signs or symptoms associated with the underlying disease that were not present before the AE reporting period
- Complications that occur as a result of protocol-mandated interventions (e.g., invasive procedures such as biopsies).

The following are NOT considered AEs:

- **Pre-existing condition:** A pre-existing condition (documented on the medical history CRF) is not considered an AE unless the severity, frequency, or character of the event worsens during the study period.
- **Pre-planned or elective hospitalization:** A hospitalization planned before signing the informed consent form is not considered an SAE, but rather a therapeutic intervention. However, if during the pre-planned hospitalization an event occurs, which prolongs the hospitalization or meets any other SAE criteria, the event will be considered an SAE. Surgeries or interventions that were under consideration, but not performed before enrollment in the study, will not be considered serious if they are performed after enrollment

in the study for a condition that has not changed from its baseline level. Elective hospitalizations for social reasons, solely for the administration of chemotherapy, or due to long travel distances are also not SAEs.

- **Diagnostic Testing and Procedures:** Testing and procedures should not to be reported as AEs or SAEs, but rather the cause for the test or procedure should be reported.
- **Asymptomatic Treatment Related Lymphocytosis:** This event should also not be considered an AE. Subjects with treatment-related lymphocytosis should remain on study treatment and continue with all study-related procedures

13.1.2. Serious Adverse Events

A serious adverse event based on ICH and EU Guidelines on Pharmacovigilance for Medicinal Products for Human Use is any untoward medical occurrence that at any dose:

- Results in death (i.e., the AE actually causes or leads to death).
- Is life-threatening. Life-threatening is defined as an AE in which the subject was at risk of death at the time of the event. It does not refer to an event which hypothetically might have caused death if it were more severe. If either the Investigator or the IND Sponsor believes that an AE meets the definition of life-threatening, it will be considered life-threatening.
- Requires in-patient hospitalization >24 hours or prolongation of existing hospitalization.
- Results in persistent or significant disability/incapacity (i.e., the AE results in substantial disruption of the subject's ability to conduct normal life functions).
- Is a congenital anomaly/birth defect.
- Is an important medical event that may not result in death, be immediately life-threatening or require hospitalization, but may be considered an SAE when, based upon appropriate medical judgment, the event may jeopardize the subject or subject may require intervention to prevent one of the other outcomes listed in this definition. Examples of such events are intensive treatment in an emergency department or at home for allergic bronchospasm, blood dyscrasias, or convulsion that does not result in hospitalization; or development of drug dependency or drug abuse.

For serious adverse events with the outcome of death, the date and cause of death will be recorded on the appropriate case report form. For deaths related to disease progression (coded to malignant neoplasm progression), the date and cause of death will be recorded on the appropriate case report form, however, the event will be considered expected for the purpose of determining expedited reporting requirements to regulatory authorities. If the cause of death is unknown at the time of reporting, "unexplained death" should be recorded on the eCRF. If the cause of death

later becomes available "unexplained death" should be replaced by the established cause of death.

For deaths related to disease progression (coded to malignant neoplasm progression), the date and cause of death will be recorded on the appropriate case report form, but the event will not be expedited as an individual case safety report (ICSR) to regulatory authorities.

13.1.3. Severity Criteria (Grade 1-5)

Definitions found in the Common Terminology Criteria for Adverse Events version 4 (CTCAE v4.03) will be used for grading the severity (intensity) of adverse events. The CTCAE version 4.03 displays Grades 1 through 5 with unique clinical descriptions of severity for each referenced AE. Should a subject experience any AE not listed in the CTCAE version 4.03, the following grading system should be used to assess severity:

- Grade 1 (Mild AE) – experiences which are usually transient, requiring no special treatment, and not interfering with the subject’s daily activities
- Grade 2 (Moderate AE) – experiences which introduce some level of inconvenience or concern to the subject, and which may interfere with daily activities, but are usually ameliorated by simple therapeutic measures
- Grade 3 (Severe AE) – experiences which are unacceptable or intolerable, significantly interrupt the subject’s usual daily activity, and require systemic drug therapy or other treatment
- Grade 4 (Life-threatening or disabling AE) – experiences which cause the subject to be in imminent danger of death
- Grade 5 (Death related to AE) – experiences which result in subject death

13.1.4. Causality (Attribution)

The Investigator is to assess the causal relation (i.e., whether there is a reasonable possibility that the study drug caused the event) using the following definitions:

Not Related: Another cause of the AE is more plausible; a temporal sequence cannot be established with the onset of the AE and administration of the investigational product; or, a causal relationship is considered biologically implausible.

Unlikely: The current knowledge or information about the AE indicates that a relationship to the investigational product is unlikely.

Possibly Related: There is a clinically plausible time sequence between onset of the AE and administration of the investigational product, but the AE could also be attributed to concurrent or underlying disease, or the use of other drugs or procedures. Possibly related should be used when the investigational product is one of several biologically plausible AE causes.

Related: The AE is clearly related to use of the investigational product.

13.2. Unexpected Adverse Events

An “unexpected” AE is an AE that is not listed in the Investigator's Brochure/package insert or is not listed at the specificity or severity that has been observed. For example, hepatic necrosis would be “unexpected” (by virtue of greater severity) if the Investigator's Brochure referred only to elevated hepatic enzymes or hepatitis. Similarly, cerebral thromboembolism and cerebral vasculitis would be “unexpected” (by virtue of greater specificity) if the Investigator's Brochure/package insert listed only cerebral vascular accidents. "Unexpected" also refers to AEs that are mentioned in the Investigator's Brochure as occurring with a class of drugs or as anticipated from the pharmacological properties of the drug but are not specifically mentioned as occurring with the study drug under investigation.

13.3. Special Reporting Situations

Special reporting situation on a study may require expedited reporting and/or safety evaluation include, but are not limited to:

- Overdose of any study drug
- Suspected abuse/misuse of a study drug
- Inadvertent or accidental exposure to a study drug
- Medication error involving a product (with or without subject exposure to the study drug, e.g., name confusion)

Occurrence of any special reporting situations should be recorded in the eCRF. If any special reporting situation meets the criteria of an AE, it should be recorded on the AEs eCRF. If the AE is considered serious, it should be recorded on the AEs eCRF as serious and should be reported on the Serious Adverse Event Report Form. The Serious Adverse Event Report Form should be sent via email or fax to Pharmacoclinics Drug Safety or designee within 15 days of awareness

